### **2.2 Secondary Objectives**

The secondary goals of this project are (1) to assess individual parts of the composite Visual Assessment Weighted Score to independently assess vision and lacrimal function after treatment, (2) to correlate visual function

to location and size of tumor over the course of treatment, (3) to identify histologic characteristics of periocular BCCA that correlate with tumor response, and (4) to characterize molecular markers that may identify opportunities for developing adjunct treatment approaches for recalcitrant tumors. An additional objective (5) is to characterize and validate the Visual Assessment Score for use in future investigations of orbital disorders.

### 3. STUDY PROTOCOL

#### 3.1 Description of the Study

In order to assess the potential of vismodegib to improve the vision- and lacrimal-related morbidities associated with orbital and periocular BCCA, this study will follow patients with globe-threatening orbital and lacrimal-threatening periocular BCCA treated with vismodegib as standard of care. The study will be prospective, open label, non-randomized, and will determine visual and lacrimal function of treated patients.

#### **Basic Protocol (see flow chart at the end of the section):**

##### ***ELIGIBILITY AND ENROLLMENT***

- 1) Patients will be enrolled based on Eligibility Criteria, Section 4.1, at which time a pre-treatment visual assessment score will be obtained as a baseline (Table 14).
- 2) Enrollment will include Informed Consent and Baseline blood tests.
- 3) Enrollment will be performed by the PI, Co-I, or qualified designee.

**Table 14: Pre-treatment Visual Assessment Score:  
(This score provides a non-weighted baseline that will be used for testing the consistency and internal validity of the Post-treatment Visual Assessment Score (Secondary Objective #5).)**

VA in affected eye of at least 20/200	0/1
Ocular Motility intact	0/1
No diplopia	0/1
Binocularity (Fusion) +/- prism	0/1
Normal tear lake, No complaint of persistent tearing	0/1
Intact lacrimal system by probing/irrigation (both canaliculi to NLD)	0/1
Patient assessment of visual function on the affected side (Poor, Fair, Good)	0/1/2
Score Maximum	8

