### **EVALUATION**

- 10) VA, diplopia, motility, and tearing are assessed at each office visit (Visual Assessment Weighted Score see **Table 15**).
- 11) Patients undergoing surgery will have their specimen assessed histologically for the presence of tumor, and used for comparison to baseline biopsy.
  - a. The presence of tumor at the surgical margin will be determined by the pathologist. Absence of tumor at the surgical margin will lead to a presumptive cure.
- 12) The **primary outcome** will be the Visual Assessment Weighted Score (Table 15) at 1 year following initiation of vismodegib or 2 (+/- 1) months after tumor excision/debulking surgery, whichever is longer.

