**Table 15: Follow-up Visual Assessment Weighted Score:**

[figure not shown]
	Score (0=No; 1=Yes)	Max Weighted score
Intact globe (no enucleation or evisceration)	0/1	20
VA within 4 Snellen lines of baseline VA or better	0/1	5
VA at 20/200 or better	0/1	5
No binocular diplopia in primary gaze	0/1	2
Fusion (Fly) +/- prism	0/1	2
No symptomatic tearing	0/1	3
Intact lacrimal system by probing/irrigation (either canaliculus to NLD)	0/1	3
Patient pleased with visual function (Poor, Fair, Good)	0/1/2	5
Total possible:	9	50

Because there are no validated measures for assessing the success of treating orbital disease, a new, non-validated measure must be used. The Visual Assessment Weighted Score (VAWS) was developed for the purpose of this study. It is made up of standard ophthalmic exam points, as well as a subjective assessment of tearing and overall patient satisfaction. Because it is a composite score, weighting is used to emphasize visual acuity and an intact globe.

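### The only stated method for validating the follow-up visual score uses the pre-treatment score, which cannot do this alone; the scheduled follow-up scores can support a preliminary validation

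*Combined protocol and SAP*

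**What the plan says.** Section 2.2 sets the objective: "An additional objective (5) is to characterize and validate the Visual Assessment Score for use in future investigations of orbital disorders". Below Table 15, the protocol acknowledges that the score was devised for this study and has not been validated.

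The one statement of method is in the caption of Table 14 (section 3.1, Eligibility and Enrollment). The non-weighted pre-treatment score, explicitly linked there to secondary objective 5, will be "used for testing the consistency and internal validity of the Post-treatment Visual Assessment Score". No statistic is named.

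Section 4.9 gives the exact binomial test for the primary endpoint, component-wise analyses, and correlation of visual function with tumor size. It assigns nothing to objective 5.

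The schedule in Table 16 (Appendix 4) has Table 14 scored once, at screening. Table 15 is scored at months 3, 6, 9 and 12 and at withdrawal of vismodegib. Response is classified every 3 months (section 3.1, Response Assessment), and tumor size is measured at each clinic visit (section 4.5). Item 10 under Evaluation adds that "VA, diplopia, motility, and tearing are assessed at each office visit", and refers to Table 15 for this.

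**The concern.** Internal consistency is judged from the items of one scale at one time. Reproducibility is judged from the same scale read twice in patients who have not changed. A single screening score on a different set of items provides neither for Table 15.

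Vismodegib, and in some patients surgery, lies between the two readings. If the scores are compared, a difference may be a true gain or loss of function, a difference in item definitions, or measurement error, and the comparison cannot separate them. In such a comparison, a score that tracks real change would tend to look inconsistent.

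What is at stake is objective 5: the evidence on which the score would be offered for later orbital studies.

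**Working it through.** **Inputs.** Item lists and weights from Tables 14 and 15; visit schedule from Table 16; sample size of 50 from sections 4.3 and 4.9.

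**1. The plan's own totals.** The printed Table 15 weights sum to 20+5+5+2+2+3+3+5 = 45. The stated total of 50 is reached only if satisfaction, scored 0/1/2, counts 5 per raw point: 45 − 5 + 2×5 = 50. The raw maximum is 7×1 + 2 = 9, as stated. Table 14 gives 6×1 + 2 = 8, as stated.

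**2. The items side by side.**

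| Table 15 item | Weight | In Table 14 |
|---|---|---|
| Globe intact | 20 | absent |
| "VA within 4 Snellen lines of baseline VA or better" | 5 | absent |
| Acuity 20/200 or better | 5 | same threshold |
| Binocular diplopia in primary gaze | 2 | any diplopia |
| Fusion | 2 | comparable |
| Symptomatic tearing | 3 | adds a normal tear lake; complaint must be persistent |
| Lacrimal patency, either canaliculus | 3 | requires both canaliculi |
| Patient's view of vision (0/1/2) | 10 at most | comparable 0/1/2 rating |
| not scored | none | motility (1 of 8 raw points) |

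- Absent from Table 14: 20 + 5 = 25, which is 25/50 = 50% (25/45 = 56% on the printed weights).
- Defined differently: 2 + 3 + 3 = 8. Together with the absent items this is 33/50 = 66% (33/45 = 73%).
- Comparable: 5 + 2 + 10 = 17 of 50.

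**3. Timing.** Table 14 precedes treatment, and every Table 15 reading follows its start. With one reading of Table 14, no patient contributes a repeat of the same scale from it.

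**4. How much the globe item decides.** An intact globe gives 20 of the 21 points needed for success. Assuming a lost globe scores 0 on both acuity items and on fusion, the most it can reach is 2+3+3+10 = 18 (13 with satisfaction at 5), which is a failure. As an illustration only, take independent items, globe preserved in 50–90%, other binary items positive in 50–70%, and satisfaction spread evenly over its three levels. The globe and acuity-change items then carry about 59–79% of the score variance. Independence is itself doubtful, because losing the globe plausibly removes the acuity and fusion points too. Item-level correlations of Table 15 would largely reflect this structure.

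**5. Data already scheduled.** Four Table 15 readings in 50 patients give at most 4×50 = 200 scorings. Section 4.7 ends participation early after surgery, or after discontinuation without restart or surgery, so the actual number will probably be lower.

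**6. Primary test.** With n = 50, rejecting a 30% success rate at 21 or more successes gives a one-sided error of 0.0478 and power of 0.899 at a 50% rate. This reproduces the stated 90%. Nothing in this point enters that calculation.

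**The case against.** The caption names no statistic and does not say that the two totals will be compared for agreement. Nor does it say that the baseline is the only tool. A baseline can legitimately be the starting point for measuring responsiveness. Sections 3.3 and 4.9 already plan component-wise analyses and correlation of visual function with tumor size, which overlap with a construct-validity analysis.

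The two absent items are also largely unavoidable omissions. Acuity relative to baseline is met by definition at baseline, and the globe item would be nearly constant if eyes are intact at entry (an assumption). Adding them to Table 14 would not help.

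The alternatives are imperfect too. Stable disease spans anything between a 30% decrease and a 20% increase in diameter, visits are 3 months apart and usually on drug, and correlations between items are a debatable standard for a deliberately weighted composite.

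Most of this stands and limits the point. A reader might infer that half of the score will go unvalidated. The 25 points show how far the item sets differ; they do not measure lost validation. A reader might also infer that objective 5 cannot be met, or that the repeated Table 15 scores are barred from it. No text excludes them.

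The objection does not supply a method. Inter-item checks at screening would describe Table 14, not Table 15. The overlapping analyses are not assigned to objective 5, and no other method for it appears.

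**Conclusion.** The point holds in limited form. The one method stated for objective 5 cannot by itself test the consistency or validity of Table 15. The screening score is taken once before treatment, lacks items worth 25 of 50 points, defines items worth a further 8 points differently, and adds motility. This is more than missing detail, because any comparison of the two scores mixes real change with inconsistency. The 50-point denominator assumes satisfaction counts 5 per raw point.

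The consequence is confined to a secondary objective. Someone might conclude that the primary analysis is compromised. The documents do not support that: the score is openly declared non-validated, and the binomial test and its power do not depend on objective 5. The change is worth making because it uses data already scheduled.

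**What to change.** In section 4.9, add an analysis for objective 5 based on the Table 15 scores at months 3, 6, 9 and 12:

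- **Construct validity and responsiveness.** Change in the weighted (50) and raw (9) scores by response group, CR/PR against PD, and correlation with tumor size and with motility.
- **Approximate stability.** Agreement between consecutive visits in patients with stable disease and no intervening surgery. Label it approximate because visits are 3 months apart and usually on drug.
- **Item-level associations.** Descriptive only, since the globe item dominates and is linked to the acuity and fusion items.

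Limit Table 14 to a baseline for change in the items the two tables share, noting the differing definitions of diplopia, tearing and lacrimal patency. State in Table 15 that satisfaction counts 5 per raw point. Amend item 10 under Evaluation so that it does not imply that Table 15 scores motility.

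The cost is wording and some analysis time, with no new data. Precision will be limited: there are at most 50 patients, and 200 scorings is a ceiling. The PD group may be small. The protocol's background figures for locally advanced disease give PD as best response in 0 of 56 to 8 of 63, or about 0 to 6 of 50 (50×8/63 = 6.3), with more if later progression counts. No inter-rater replicate is scheduled. The report should therefore claim preliminary validation only.

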## **RESPONSE ASSESSMENT**

- 5) Assess response by ophthalmic exam at 3 month intervals or at time of early discontinuation of vismodegib (by treating physician or qualified designee), + MRI or CT with contrast at 5 and once in the timeframe from 9-12 months (+/- 1 month) and clinical photography.
- 6) Treatment response will be determined per Response Evaluation Criteria in Solid Tumors (**RECIST**) protocol, using clinical measurements and/or tumor imaging measurements (determined by treating physician):
  - i. Complete response (CR) = complete disappearance of tumor
  - ii. Partial response (PR) = at least 30% decrease in largest diameter
  - iii. Progressive disease (PD) = at least 20% increase in largest diameter
  - iv. Stable disease (SD) = neither PR nor PD
- 7) Determination of whether the tumor is progressing (PD) vs. responding (SD, PR or CR) will be done at regular intervals (3 months), until 1 year after initiation of vismodegib treatment. Following the 1 year mark, patients will continue to be followed per SOC.

## **OUTCOME ASSESSMENT**

- 8) The **PRIMARY OUTCOME** will be determined by analyzing visual function per **Table 15** at 1 year following initiation of vismodegib treatment or at 2 months +/- 1 month following surgery, whichever is longer (i.e. final assessment may be extended up to 15 months following initiation of vismodegib). **A weighted score of at least 21 out of possible 50 would constitute a successful treatment outcome.**

- 9) **SECONDARY OUTCOMES will be assessed via subgroup analysis:**
- a. If the tumor progresses (PD) while on vismodegib treatment, then treating physician may discontinue vismodegib and offer surgical resection or debulking per SOC → **OUTCOME #1 (Progressive Disease)**.
  - b. If patient refuses surgical option, then continue monitoring patient.
  - c. Patients with stable or shrinking tumors (CR, PR or SD) will be considered “**Responders**.”
  - d. If the tumor responds within the first year of treatment and patient tolerates side effects (per patient), CONTINUE vismodegib therapy and monitoring until the end of the study → **OUTCOME #2 (SD, PR or CR and good tolerance)**
  - e. If patient reports subjectively intolerable side effects (per patient), then discontinue vismodegib, and treating physician can offer surgical resection or debulking → **OUTCOME #3 (SD, PR or CR and poor tolerance)**.
  - f. If patient refuses surgical options, continue monitoring.
  - g. A treatment break, or “drug holiday” will not be offered as an option as part of this study.
  - h. If treatment with vismodegib is stopped but the patient later decides to restart vismodegib, then the patient’s exam findings at termination of treatment will be used for assessing the primary outcome. The patient can continue to be followed as part of the study, and additional exam findings can be used for secondary outcome assessment.

### **EVALUATION**

- 10) VA, diplopia, motility, and tearing are assessed at each office visit (Visual Assessment Weighted Score see **Table 15**).
- 11) Patients undergoing surgery will have their specimen assessed histologically for the presence of tumor, and used for comparison to baseline biopsy.
  - a. The presence of tumor at the surgical margin will be determined by the pathologist. Absence of tumor at the surgical margin will lead to a presumptive cure.
- 12) The **primary outcome** will be the Visual Assessment Weighted Score (Table 15) at 1 year following initiation of vismodegib or 2 (+/- 1) months after tumor excision/debulking surgery, whichever is longer.

**Table 15: Follow-up Visual Assessment Weighted Score:**

[figure not shown]
	Score (0=No; 1=Yes)	Max Weighted score
Intact globe (no enucleation or evisceration)	0/1	20
VA within 4 Snellen lines of baseline VA or better	0/1	5
VA at 20/200 or better	0/1	5
No binocular diplopia in primary gaze	0/1	2
Fusion (Fly) +/- prism	0/1	2
No symptomatic tearing	0/1	3
Intact lacrimal system by probing/irrigation (either canaliculus to NLD)	0/1	3
Patient pleased with visual function (Poor, Fair, Good)	0/1/2	5
Total possible:	9	50

Because there are no validated measures for assessing the success of treating orbital disease, a new, non-validated measure must be used. The Visual Assessment Weighted Score (VAWS) was developed for the purpose of this study. It is made up of standard ophthalmic exam points, as well as a subjective assessment of tearing and overall patient satisfaction. Because it is a composite score, weighting is used to emphasize visual acuity and an intact globe.

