### Analysis

Treatment outcome (Visual Function Score; Table 15) will be measured overall (primary endpoint). The **primary** outcome will be the assessment of the visual system using a weighted assessment scale per Table 15. A weighted score of 21 or more (out of possible 50) constitutes a successful outcome.

Exact binomial one-sided tests will be used to compare success rate of the primary outcome (Visual Function Score, Table 15) to 30% (a literature- and practice-based estimate of the loss of visual and lacrimal function after treatment of locally advanced periocular/orbital BCCA). If the true success rate is 50%, the study will have 90% power to reject the null hypothesis ( $p=0.3$ ) in favor of the alternative ( $p>0.3$ ) at  $\alpha=0.05$ .

Secondary endpoints will utilize the three treatment modality groups:

- #1: treatment stopped due to non-response (per RECIST);
- #2: treatment continued for a full year with good response and good tolerance
- #3: treatment stopped due to poor tolerance in spite of good response;

**Secondary** outcomes will utilize the actual numerical values obtained during the assessment over time to correlate visual function with tumor size (measured at each visit and/or via MRI/CT imaging). The secondary outcome measures will assess each part of the composite visual assessment score to determine changes in vision and lacrimal function following vismodegib treatment.

Histologic characteristics and molecular markers to be studied for the secondary objective include HMW keratin, proliferation markers such as Ki67, hedgehog and Wnt pathway markers. These will be summarized overall, by treatment modalities, and by outcome groups (e.g., Good or Poor Visual or Lacrimal Function). No other subgroup analyses are planned. **Please see page 20, BASIC RESEARCH ARM.**

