### **Determination of Sample Size**

- *Endpoints used*

The endpoint used for determining sample size was a Visual Assessment Weighted Score of at least 21 (out of possible 50).

- *Methodology used*

The exact binomial one-sided test with  $n=50$  has 90% power to reject the null hypothesis  $p=0.3$  in favor of the alternative  $p=0.5$  at  $\alpha=0.05$ .

A recruitment assessment will be performed at the 2 and 3 year time points (out of 4 years), in order to assess recruitment. The goal of the study is to enroll 50 patients over 3 years, or 16-17 patients per year. After year 1, if recruitment drops below a minimum 12 patients (or at least one per month on average) then the study will be adjusted by (1) extending the trial beyond 3 years of recruitment, and/or (2) extending patient recruitment to outside medical institutions. After year 2, if recruitment is greater than 20 but below 30 patients, then the trial will be extended by 1 year. If recruitment is below 20 patients at the end of year 2 then the trial will be both extended by 1 year and patient recruitment extended to outside institutions.

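### Two Table 15 items can misstate the component results: the diplopia item credits a removed or blind eye, and the four-line acuity item has no chart, floor or off-chart rule

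*Combined protocol and SAP*

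**What the plan says.** Table 15 (section 3.1) is a sum of weighted items, and 21 of 50 is a success. Four items matter here:

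- "No binocular diplopia in primary gaze", 2 points. No rule is given for an eye that has been removed or cannot see.
- "VA within 4 Snellen lines of baseline VA or better", 5 points. No chart, line size, floor or off-chart rule is given.
- A separate 5-point item for acuity of 20/200 or better.
- The globe item, "Intact globe (no enucleation or evisceration"), 20 points.

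Poor baseline vision is foreseen: section 4.1 sets no minimum acuity, and Table 14 has a baseline item that eyes below 20/200 fail. Table 14 also scores diplopia at baseline.

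The items are results in their own right. Secondary objective 1 assesses the parts of the score individually, and section 4.9 (Analysis) states: "The secondary outcome measures will assess each part of the composite visual assessment score to determine changes in vision and lacrimal function". Section 4.9 also correlates recorded numerical values of visual function with tumor size, without saying how Snellen acuity becomes a number. It places all enrollees in an intent-to-treat analysis.

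For the primary outcome, "Exact binomial one-sided tests will be used to compare success rate of the primary outcome" with a null rate of 30%. Under Determination of Sample Size, the test with 50 patients "has 90% power to reject the null hypothesis" if the true rate is 50%.

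**The concern.** A component result should get worse when the patient does. The diplopia item can do the opposite. Binocular diplopia needs two seeing eyes, so a patient who had diplopia at entry and then lost the eye moves from not met to met and looks like an improvement.

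The acuity item has a different weakness. Lines on a Snellen chart are not equal steps, and the chart ends. The same 5-point credit can therefore stand for different losses, depending on the chart used and on where the patient starts. Near the bottom of the chart the item has no stated meaning.

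The study is single-arm, so no control group shares these scoring effects. Secondary objective 5 is to validate the score for later use, so undefined items would be carried forward.

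**Working it through.** **1. The plan's own figure.** Inputs from section 4.9: n = 50, null 0.30, alternative 0.50, one-sided alpha 0.05, exact binomial. The critical count is the smallest r with P(X ≥ r | 0.30) ≤ 0.05. P(X ≥ 20) = 0.0848 and P(X ≥ 21) = 0.0478, so r = 21 patients. (This count only happens to equal the score threshold of 21 points.) Power = P(X ≥ 21 | 0.50) = 0.8987. The stated 90% reproduces, and nothing below changes it.

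**2. Diplopia component.** Let k be the number of the 50 patients whose affected eye is removed or blind, and p the diplopia-free proportion among the rest. Neither is given in the documents.

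- Rate as worded: [p(50 − k) + k]/50.
- Rate with those eyes scored as not met: p(50 − k)/50.
- Difference: k/50. For k = 1, 2, 5, 10 this is 2, 4, 10, 20 percentage points, whatever p is.
- Against a rate computed only in patients with two seeing eyes, the excess is k(1 − p)/50. For k = 1 this is 0.4 points at p = 0.80 and 0.8 points at p = 0.60 (both assumed).

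**3. Can the diplopia credit reach the primary threshold?** The items other than satisfaction sum to 20 + 5 + 5 + 2 + 2 + 3 + 3 = 40, so the printed total of 50 requires satisfaction to count up to 2 × 5 = 10.

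- Removed eye, with globe, both acuity items and fusion at 0: diplopia 2 + tearing 3 + lacrimal 3 + satisfaction 10 = 18 (13 if satisfaction is capped at 5). Both are below 21.
- Retained but blind eye: globe 20 + diplopia 2 = 22. Without the diplopia credit this patient has 20 and passes only if another item is met, for example tearing (20 + 3 = 23). The credit is decisive only when nothing else is met.

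**4. Acuity item.** Loss in logMAR = log10(final denominator / baseline denominator), four lines apart. The charts are assumptions, because the documents name none.

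| Assumed chart (20/x) | Smallest four-line loss | Largest on-chart four-line loss | Four lines leave the chart from |
|---|---|---|---|
| 20, 25, 30, 40, 50, 70, 100, 200, 400 | 20 to 50: log10(2.5) = 0.40 | 50 to 400: log10(8) = 0.90 | 20/70 |
| The same plus 60 and 80 | 40 to 80: log10(2) = 0.30 | 70 to 400: log10(5.71) = 0.76 | 20/80 |
| The second plus 125, 150 and 300 | 40 to 80: 0.30 | 125 to 400: log10(3.2) = 0.51 | 20/150 |

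From a 20/200 baseline, every acuity still readable on any of the three charts is within four lines. Below the last line the item is silent.

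**The case against.** The case for leaving Table 15 alone has force. The score is openly described as non-validated. The diplopia item is worth 2 of 50 points, and a removed eye also scores 0 on the globe and fusion items, which are reported beside it. A nearly blind eye fails the separate 20/200 item. An eye that was off the chart at entry and has not changed is correctly maintained on a baseline-relative item. All of this stands and limits the harm. It does not correct the diplopia component, or the maintained-acuity component, when either is read alone, as the plan intends.

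Several stronger inferences are tempting, but the documents do not support them:

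- *An exenterated patient scores 20 + 2 = 22 and is a success.* This reads the parenthesis of the globe item as a complete list. The item is headed as an intact globe, and an exenterated orbit has none, so the natural score is 0. Exenteration is simply not named.
- *Eyes that fall off the chart are credited.* The text is silent. Counting fingers is not a Snellen line, so an assessor could equally score the item as not met.
- *A removed eye with an off-chart baseline reaches 23.* This adds 5 to the 18 above, and it requires a removed eye to be given an acuity within four lines of baseline. Nothing in the table says so.
- *The item spans a 2-fold to 8-fold loss.* That joins the minimum of one assumed chart to the maximum of another. Chart by chart the spans are 2.5- to 8-fold, 2- to 5.7-fold and 2- to 3.2-fold.
- *Snellen fractions will be treated as an interval scale.* Section 4.9 does not say this. It only omits the conversion.

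**Conclusion.** The concern holds for two items and for the component analyses. As worded, the diplopia item credits a removed or blind eye, which adds 2 percentage points per patient compared with scoring it as not met. The acuity item leaves open how large a loss counts as maintained (0.30 to 0.90 logMAR across the three assumed charts, less within any one of them) and whether a nearly blind eye qualifies.

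This is a risk of unknown size. The documents give no eye-removal rate, no distribution of baseline acuity and no chart. The diplopia credit alone cannot turn a removed eye into a primary success. It can tip a retained blind eye only in the narrow case where no other item beyond the globe is met. Sample size and power stand as stated. The exenteration wording is a clarification, not an error in scoring.

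**What to change.** In Table 15 and section 4.9:

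- **Diplopia.** Keep all enrollees and score the item 0 when the affected eye is removed or has no light perception. Show results among patients with two seeing eyes only as a supplement, because that subset is selected on outcome.
- **Acuity.** Name the chart. Convert recorded acuity to logMAR with fixed, pre-stated values for counting fingers, hand motion, light perception and no light perception. Define maintained as a stated logMAR loss, for example no more than 0.4 (four lines on an equal-step chart). Score 0 if the eye is removed or has newly lost light perception. Use logMAR in the tumor-size analyses.
- **Globe (clarification only).** Word the item to cover any removal of the eye, including exenteration.

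The cost is wording on the scoring sheet and in the analysis section, since acuity is already part of the ophthalmic exam. The downside is that fewer eyes with poor baseline vision will count as maintained: with a 0.4 limit, a fall from 20/70 to 20/200 fails (log10(200/70) = 0.46), although it is only two lines on the first assumed chart. The 0.4 limit is a choice that the study team should confirm. Because Table 15 also yields the primary outcome, the rules should be fixed before outcomes are scored.

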## **2. STUDY OBJECTIVES**

### **2.1 Primary Objectives**

The primary goal of this project is to determine whether treatment with vismodegib of patients with locally advanced or recurrent orbital and/or periorbital BCCA will be associated with good ophthalmic outcomes, as measured using a novel Visual Assessment Weighted Score (Table 15). The primary objective emphasizes globe preservation and maintenance of visual acuity, and a score of 21 or greater (out of 50) will be considered a good outcome.

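### Table 15: the maximum weighted scores add to 45, not the stated 50, and the points for patient satisfaction are not set out

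*Combined protocol and SAP*

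**What the plan says.** Table 15 (section 3.1) has eight items, a raw-score column, and a second column headed as the maximum weighted score. Seven items are coded 0/1, with entries 20 (intact globe), 5 and 5 (two acuity items), 2 (no diplopia), 2 (fusion), 3 (no tearing) and 3 (lacrimal patency). The eighth, "Patient pleased with visual function (Poor, Fair, Good"), is coded 0/1/2 and has the entry 5. The total row gives 9 raw and 50 weighted. The text below the table explains that "weighting is used to emphasize visual acuity and an intact globe".

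The figure of 50 recurs in five places:

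- Section 2.1: "a score of 21 or greater (out of 50) will be considered a good outcome".
- Section 3.1, Outcome Assessment, item 8: "A weighted score of at least 21 out of possible 50 would constitute a successful treatment outcome". Section 3.3 has the same sentence.
- Section 4.9, Analysis: "A weighted score of 21 or more (out of possible 50) constitutes a successful outcome".
- Section 4.9, Determination of Sample Size: "a Visual Assessment Weighted Score of at least 21 (out of possible 50").

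Secondary objective 5 (section 2.2) is "to characterize and validate the Visual Assessment Score for use in future investigations of orbital disorders". The note to Table 14 says that the baseline score will be "used for testing the consistency and internal validity of the Post-treatment Visual Assessment Score".

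**The concern.** A column of maxima should add to the stated maximum, and this one falls 5 short. The raw column's key defines only 0 and 1, so it does not explain a raw score of 2. The available text gives no weighted points for the fair or good ratings and does not call the entries multipliers.

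Two careful scorers could therefore differ. One follows the heading, caps the item at 5 and has to invent a value for the fair rating. The other works back from 50 and scores 0/5/10. The protocol describes the instrument as new and not validated, so it offers no established scoring rule to settle the matter. At stake are the numeric total, the weight of satisfaction relative to acuity, and possibly the success call at 21.

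**Working it through.** **Inputs.** Item codes, entries and totals are from Table 15. The cut-off of 21 is from sections 2.1, 3.1, 3.3 and 4.9. The design figures (n = 50, 30% against 50%, one-sided 5%) are from section 4.9.

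**Totals**

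- Raw: 7 × 1 + 2 = 9, as printed. Table 14 works the same way (6 × 1 + 2 = 8, as printed), so satisfaction counts as 2 raw points in both tables and no row appears to be missing.
- Weighted, by the heading: 20 + 5 + 5 + 2 + 2 + 3 + 3 + 5 = 45. The printed 50 is not reproduced.
- Weighted, as raw maximum × entry: 40 + 2 × 5 = 50. The printed 50 is reproduced.

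For the seven 0/1 items, weight and maximum are the same number, so only satisfaction separates the readings.

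**Size on the numeric score**

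| | Weight per point | Item maximum |
|---|---|---|
| Good | 10 | 5 |
| Fair | 5 | 2.5 if linear (assumption; range 0 to 5) |
| Total possible | 50 | 45 |
| Satisfaction share | 10/50 = 20% | 5/45 = 11% |
| Both acuity items | 10 | 10 |

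Satisfaction counts as much as the two acuity items together under the first reading, and half as much under the second.

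**Effect on the success call.** Item patterns were enumerated under 0/5/10 and under 0/Fair/5. The counts are patterns, not patient frequencies.

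- *Globe intact:* 2⁶ × 3 = 192 patterns. The globe gives 20, so one more point is enough. Under 0/5/10, 191 succeed; the exception is every other item at 0 with a poor rating. Under 0/Fair/5, the same 191 succeed if Fair is worth at least 1 point. If Fair is worth less than 1, one pattern changes (at Fair = 0, 25 against 20).
- *Globe lost, 20/200 and fusion scored 0, no binocular diplopia scored 1:* 2³ × 3 = 24 patterns. One changes, for any Fair from 0 to 5: 5 (within 4 lines of baseline) + 2 + 3 + 3 = 13, plus Good = 23 (success) or 18 (failure).
- *The same, with the within-4-lines item also 0:* the highest possible total is 2 + 3 + 3 + 10 = 18, so nothing changes.
- *Globe lost, no restriction on the other items:* with Fair at 2.5, 26 of 192 patterns change. Each needs at least one acuity item credited to the lost eye, so most are clinically implausible.

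**Power.** The exact one-sided test with n = 50 rejects at 21 or more successful patients (the match with the score cut-off is a coincidence). Its true alpha is 0.0478 and its power at 50% is 0.8987. The stated 90% reproduces and does not depend on Table 15.

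**The case against.** The best reply is that the table resolves itself. The raw codes, the raw total of 9, the weighted total of 50 and five repetitions of 50 all point to 5 per raw point, which gives 0/5/10 directly. On that view only a loose heading remains. The linear value for the fair rating matters only under the less likely reading. The primary endpoint is dichotomous and hardly moves, and the documents specify no analysis for objective 5 that uses the weighted total. Both readings also fit the stated emphasis on globe and acuity: those items make up 30/50 = 60% or 30/45 = 67% of the maximum. Finally, a figure next to Table 15 is missing from the available text and might have given the points.

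Much of this stands. The per-point reading is the more likely one, the consequence is limited, and the emphasis sentence does not decide between the readings. Sections 3.3 and 4.9 plan to correlate numeric visual function with tumour size but do not say that the weighted total is used, so an effect there is possible rather than shown. The missing figure qualifies the statement that the points are not given.

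None of it makes a column headed as maxima add to 50. A scorer who follows the printed heading still gives a good rating 5 points fewer than the 50-point scale requires.

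**Conclusion.** The concern holds. As printed, Table 15 is internally inconsistent: 45 by its column heading, 50 by its total row and the rest of the protocol. The likely fault is the heading and the satisfaction entry.

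The numeric total differs by 5 points for every patient with a good rating, and by 2.5 for a fair rating if a maximum of 5 is scored linearly. This affects any use of the weighted total, above all its characterisation and validation. Analyses of single components are unaffected.

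The success call is essentially unaffected. That rests on two assumptions: the fair rating is worth at least 1 point, and acuity items are not normally credited once the globe is lost. Sample size and power are unaffected. The table should be corrected because it defines the primary outcome, but the error does not threaten the primary test.

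**What to change.** Before analysis, the sponsor should confirm which reading was intended and amend the protocol in one of two ways:

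- **If 50 is intended** (this fits the rest of the document): head the column as a weight per point and show satisfaction as 0/5/10, with a maximum of 10. This changes one heading and one cell.
- **If a maximum of 5 is intended:** state the weighted points for the fair rating, and change 50 to 45 in Table 15 and in the five places listed above. A cut-off kept at 21 would then be 21/45 = 47% of the maximum instead of 21/50 = 42%, so the sponsor should say whether that is acceptable.

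In either case, state what the raw scores 0, 1 and 2 mean for this item, and recompute any recorded totals from the item scores. No new data are needed, because items are recorded as 0/1 or 0/1/2.
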